MI-SI Training. Training will consist of sixteen hours. It will consist of 8 hours of training in general MI followed by eight hours of MI-SI training. Training modalities include listening to power-point presentations, selected readings from the MI text  and the MI-SI manual (included in Appendix), MI exercises, and listening to and discussing recorded examples of MI-SI. The PI will observe the first two interviews to ensure that therapists meet MITI fidelity criteria and provide corrective feedback. Additional training activities will be scheduled as necessary.

MI-SI Supervision. An RCT evaluating methods for training MI clinicians found that ongoing coaching and/or feedback is needed to maintain proficiency in MI.  The PI will provide weekly supervision for MI-SI clinicians, focusing on promoting the fidelity of MI-SI by discussing

difficult cases, listening to and discussing recorded MI-SI interviews, and reviewing MI materials and publications.

**Interview Coding and Training.** MI-SI sessions will be recorded and coded for fidelity using the MITI,  which requires specialized training.

MITI Coding and Training. The MITI is a behavioral coding system that is used to code 20-minute samples of tape for adherence to MI principles (e.g. empathy, autonomy support) and use of specific MI techniques (e.g. reflections, open questions). Summary values from coded interviews will be used to assess fidelity,  and provide material for supervisory sessions. A random selection of interviews will be double-coded and inter-rater reliability will be computed using inter-class correlation coefficients. 

The PI will provide MITI training to the research assistants who are coding the MI-SI therapy sessions. The protocol that will be used is identical the one use by [name]., an MI Training expert who trained coders for Project MATCH,  and trained the PI. Training will consist of eight hours and include reviewing the MITI coding scale, coding MI interviews and comparing the codes to "gold standard" codes available on the MI website,  and coding recordings of MI-SI interviews. Coders will be considered reliable when they achieve reliabilities of good or better (ICC > .60) on 80% of MITI codes. 

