#### Warm Transfer Process

- 1. Press the **conference** button.
- 2. Dial [name] press option 1 and a Crisis Line responder will answer.
- 3. Describe the participants risk and provide name and telephone number.
- 4. Pressing the **conference** button and participants will be linked with Crisis Line counselors.

It is possible that participants may refuse to be transferred to the Crisis Line or hang up. As a result, research clinicians will ask participants to use a landline for MI-SI telephone sessions so that the number can be tracked to an address if emergency services are needed. For participants who only have a cell phone, interviewers will begin each session by asking the participant for the address from which they are calling so that the clinician can send help if it is needed. Because participants may give a false address, clinicians will consult with Crisis Line responders who have a protocol for emergency responses for cell phone callers.

Adverse Events (AE). All suicide attempts and episodes of imminent risk that require intervention will be considered adverse events and will be addressed according to IRB regulations. The determination of an AE will be made by an investigator other than the PI (i.e., [name] or [name]), to reduce the possibility of bias. Syracuse VA IRB also requires that serious adverse events, any event leading to a deviation from the protocol such as emergency hospitalization (e.g., to address acute suicidality) or death, be reported to the principal investigator within 24 hours, who is required to report them to the IRB within 48 hours. Adverse events that are minor such as temporary distress will be recorded by interviewers and reported to the IRB annually. All adverse events will be reported to the principal investigator within 24 hours to establish the level of significance and determine the appropriate procedure.

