### **Data Monitoring Committee**

The Centralized CSR&D Data Monitoring Committee (DMC) will be providing additional oversight for the project and function as a Data Safety Monitoring Board (DSMB). The DMC is charged with guiding the safe scientific and ethical conduct of projects. At least once a year, the PI will send information to the DMC on recruitment progress, participant retention, and progress of data management and analyses. Serious adverse events and unanticipated problems are reported to the DMC as they occur. DMC recommendations on study performance, continuation or alteration of a protocol, and participant safety strategies or concerns are formulated after each data reassessment and forwarded to the PI and ACOS/R of each site. The DMC may consider study performance to be sufficiently poor that the project should be placed on probation, and specific conditions associated with continuation. The DMC may recommend study termination in some circumstances. Local institutional rules for conducting research and reporting issues to the facility R&D Committee and/or IRB are not changed by being monitored simultaneously by a centralized DMC. Upon receipt of the report, the PI will be responsible for transmitting a copy of the report to the IRB.

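### A non-PI investigator decides what counts as an adverse event, but classifying its seriousness appears to fall to the PI who supervises the therapy, so the bias safeguard is incomplete

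*Combined protocol and SAP*

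**What the plan says.** The Adverse Events paragraph (Human Subjects, at the end of the Warm Transfer Process text) has five relevant elements, in this order:

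- Suicide attempts, and imminent-risk episodes needing intervention, are AEs by definition and are handled under IRB regulations.
- "The determination of an AE will be made by an investigator other than the PI", and the reason given is "to reduce the possibility of bias".
- The local IRB's serious category is described as "serious adverse events, any event leading to a deviation from the protocol such as emergency hospitalization" or death. The PI must hear of these events inside 24 hours and is described as the person "who is required to report them to the IRB within 48 hours".
- A slower route is set for lesser events: "Adverse events that are minor such as temporary distress will be recorded by interviewers and reported to the IRB annually". No other timing is given for them.
- The paragraph closes with a rule that covers every AE: "All adverse events will be reported to the principal investigator within 24 hours to establish the level of significance and determine the appropriate procedure".

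Elsewhere, under MI-SI Supervision in General Procedures, "The PI will provide weekly supervision for MI-SI clinicians", which includes discussing difficult cases and listening to recorded sessions. The Data Monitoring Committee section says that serious adverse events and unanticipated problems go to the DMC when they happen. It does not say who decides that an event belongs in either category.

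**The concern.** By excluding the PI from the first decision, the plan accepts that the PI's judgement on safety events could be biased. The next decision, how significant the event is, appears to return to the PI, and in this plan that decision sets how fast the event is reported. The PI is responsible for the delivery of the experimental therapy and, through supervision and recordings, will know the arm for many MI-SI events.

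At stake is the speed and even-handedness of safety reporting. A borderline event in the MI-SI arm could be treated as minor by someone close to that arm, and neither the IRB nor the DMC would then see it promptly. Even if this never happens, the trial could not show that it was prevented.

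**Working it through.** The plan gives no figure for this point, so there is nothing to recompute. The check is a comparison of the provisions.

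1. **Is there an AE?** A non-PI investigator decides. Suicide attempts are AEs by definition, which leaves this person little to decide about them. For imminent-risk episodes the decision is real, because the episode must have required intervention to count.

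2. **How significant is it?** The closing sentence of the paragraph has all AEs reported to the PI for this purpose. The sentence is passive and does not name who sets the level. The PI is the natural reading, since the events go to the PI so that the level can be set. No other section gives the step to the non-PI investigator, the DMC or anyone else independent of the therapy.

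3. **What follows from the level?** Two timed routes are stated:
   - serious: to the PI within 24 hours, to the IRB within 48 hours, and to the DMC when it happens;
   - minor: to the IRB once a year.

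4. **Where is there room for judgement?** Deaths and emergency hospitalizations are named as serious, and temporary distress is named as minor. Between these lie events that are AEs but match none of the named examples:
   - a suicide attempt that does not lead to emergency hospitalization;
   - an imminent-risk episode on a follow-up call that is resolved by transfer to the Crisis Line (Telephone Safety Plan).

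   Whether either led to a deviation from the protocol, which is the stated test for serious, is a matter of judgement. Such events are foreseeable: the Human Subjects section says suicidal behavior is expected in this sample.

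5. **Is the person in step 2 independent of the therapy?** On the natural reading, no. The PI trains and supervises the MI-SI clinicians, observes each therapist's first interviews and reviews recordings.

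The independent role therefore covers step 1 and, as written, does not extend to step 2, where the reporting route for the events in step 4 is chosen.

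**The case against.** The best defence has four parts.

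*The steps are separable.* Identifying an AE and grading it are different tasks, so assigning them to different people is not inconsistent. This stands. A reader might infer that the paragraph contradicts itself, but the text does not support that.

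*Discretion is limited by rule.* A reader might infer that every AE is open to downgrading. That goes too far: deaths and emergency hospitalizations are serious by the plan's own definition, and attempts and imminent-risk episodes are subject to IRB regulations, which may close part of the gap. Those regulations are not reproduced, so how much they close cannot be judged. The gap is confined to events between the named examples.

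*The DMC has its own sources.* Unanticipated problems reach it promptly without an SAE label. This helps in part, but an event type that the protocol calls expected is hard to bring under that heading. A reader might also infer that the PI controls the DMC's safety data. The documents do not say so: "the PI will send information to the DMC on recruitment progress, participant retention, and progress of data management and analyses" covers study conduct, and the sentence on safety reports names no sender.

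*Harm can be seen in other data.* Blinded assessors collect the C-SSRS at 1, 3 and 6 months, suicidal behavior is compared by arm, and charts are reviewed for the six months after discharge. Grading an event as minor does not remove it from the final evidence. This stands for the analysis, but these sources are not described as real-time safety monitoring.

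**Conclusion.** The concern holds as an incomplete safeguard. The plan protects the decision that an AE occurred but gives no independent person the decision on its seriousness. For events that are neither deaths nor emergency hospitalizations, that second decision separates 48-hour IRB reporting with prompt DMC reporting from an annual IRB report. It should be corrected, but it does not threaten the primary analysis.

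The conclusion rests on two assumptions: that the PI is the person who sets the level of significance, and that the IRB rules the plan refers to do not already assign this step to someone else.

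The size can be stated only as the difference between the two reporting routes. A reader might convert a full year's delay into participants enrolled meanwhile. That would require an event to be downgraded, the whole year to be lost, and prompt reporting to have halted enrolment; the documents support none of these. A reader might also link the grading to the Power Analysis provision for two-sided testing if harm is a concern. That provision does not say who forms the concern or on what evidence, so the link is conjecture. Nothing here suggests improper conduct.

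**What to change.** Amend the Adverse Events paragraph to state that:

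- the non-PI investigator who determines that an event is an AE also classifies it as serious or minor;
- the classification is recorded and dated before PI review, and made without arm information where feasible;
- the PI is still notified within 24 hours and still reports serious events to the IRB within 48 hours;
- if the PI disagrees with the classification, the disagreement is forwarded with the report.

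The closing sentence should then say that AEs go to the PI for notification and reporting, so that it no longer implies that the PI sets the level.

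The cost is a few lines of protocol text and a dated entry on the AE form. The plan already designates the investigators. The practical burden is that one of them must be reachable within the existing 24-hour limit. Sample size, visits and analyses do not change. A fully redacted event narrative or a separate relatedness grade would be optional additions and is not needed to close the gap.

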### **Data Monitoring Committee**

The Centralized CSR&D Data Monitoring Committee (DMC) will be providing additional oversight for the project and function as a Data Safety Monitoring Board (DSMB). The DMC is charged with guiding the safe scientific and ethical conduct of projects. At least once a year, the PI will send information to the DMC on recruitment progress, participant retention, and progress of data management and analyses. Serious adverse events and unanticipated problems are reported to the DMC as they occur. DMC recommendations on study performance, continuation or alteration of a protocol, and participant safety strategies or concerns are formulated after each data reassessment and forwarded to the PI and ACOS/R of each site. The DMC may consider study performance to be sufficiently poor that the project should be placed on probation, and specific conditions associated with continuation. The DMC may recommend study termination in some circumstances. Local institutional rules for conducting research and reporting issues to the facility R&D Committee and/or IRB are not changed by being monitored simultaneously by a centralized DMC. Upon receipt of the report, the PI will be responsible for transmitting a copy of the report to the IRB.

# Potential Benefit of the Proposed Research to the Subject and Others

There may or may not be direct benefits to participants. However, participants at elevated risk for suicide will be identified so that the issue can be addressed during treatment and at follow-up. Knowledge resulting from the research may also contribute to the prevention of Veteran suicides.

